- Baseline (at randomization or prior to the start of protocol treatment including Day 1 of cycle 1): PROMIS Profile-29, PRO-CTCAE, EQ-5D (5L)
- End of each treatment cycle (starting with cycle 1): PRO-CTCAE, EQ-5D (5L),
- End of first treatment cycle (6 weeks, can be measured on Day 1 of cycle 2): PRO-CTCAE, EQ-5D (5L), PROMIS Profile-29
- End of second treatment cycle (3 months, can be measured on Day 1 of cycle 3): PRO-CTCAE, EQ-5D (5L), PROMIS Profile-29
- Disease Stability (6 months; can be measured on Day 1 of cycle 5): PRO-CTCAE, EQ-5D (5L), PROMIS Profile-29

Long-Term Follow-up (for patients starting at least one dose of protocol treatment and not receiving any non-protocol therapy)

regardless of still receiving any protocol treatment (All study arms, indexed to study entry)

- EQ-5D (5L): every 3 months from study entry up to 2 years
- PROMIS Profile-29: at 6 weeks, 3 months and 6 months from study entry, then every 6 months up to 2 years

Ad-Hoc Assessments (End of Treatment in Each Step, Dose Modification)

- End of Step 1 Treatment (before crossover, for any reason including Section [5.9.2.2](#)): PROMIS Profile-29, PRO-CTCAE, EQ-5D (5L)
- End of Step 2 Treatment (after crossover, for any reason including Section [5.9.2.2](#)): PROMIS Profile-29, PRO-CTCAE, EQ-5D (5L)
- Dose Modification (Section [5.4](#)): PRO-CTCAE, EQ-5D (5L)

Second Treatment (Crossover, Arms C, D, indexed to second treatment)

- Baseline (at randomization or prior to the start of protocol treatment including Day 1 of cycle 1): PROMIS Profile-29, PRO-CTCAE, EQ-5D (5L)
- End of each treatment cycle (starting with cycle 1): PRO-CTCAE, EQ-5D (5L)
- End of first treatment cycle (6 weeks, can be measured on Day 1 of cycle 2): PRO-CTCAE, EQ-5D (5L), PROMIS Profile-29
- End of second treatment cycle (3 months, can be measured on Day 1 of cycle 3): PRO-CTCAE, EQ-5D (5L), PROMIS Profile-29
- Disease Stability (6 months; can be measured on Day 1 of cycle 5): PRO-CTCAE, EQ-5D (5L), PROMIS Profile-29

Assessments

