We will conduct PRO assessments in regular, clinically informative intervals to evaluate short-term and long-term toxicities and functional impact for each treatment. We will assess all PROs at study randomization to provide the overall baseline scores to evaluate change across initial treatment, and long-term follow-up. We will evaluate treatment sequence by using the overall baseline assessment at randomization for treatment 1 and the initiation of treatment 2 (after progression and washout period) for baseline assessments.

During initial and secondary treatment periods, we will measure patient-reported toxicities (PRO-CTCAE) and overall health (EQ-5D (5L)) at each clinical visit where adverse events (CTCAE) are evaluated. Broader measures of physical and mental function (PROMIS Profile-29) will be collected at important clinical points: at six weeks (end of cycle 1), three months (end of second cycle), and 6 months (disease stability).

We will conduct all long term follow-up assessments (regardless of still on study treatment given no non-protocol treatment has been

administered) indexed to study entry every 3 months up to 2 years. EQ-5D (5L) assessments will be collected more frequently to coincide with the adverse events assessment (by CTCAE, every 3 months) until year 2. These additional assessments will be used to provide toxicity severity informing our primary 2-year PRO endpoint.

Throughout the study period we will conduct additional ad-hoc assessments for the following situations that may occur: end of treatment in each step (before crossover and after crossover). We will administer PRO-CTCAE and EQ-5D (5L) at the start of all dose modifications (Section [5.3](#)).

End of step 1 treatment and subsequent enrollment into step 2 treatment will trigger two assessments. One at the point end of step 1 treatment is documented, and a separate assessment at the initiation of secondary treatment after washout (treatment 2 baseline). Assessments will also be administered at the point end of step 2 treatment (after crossover) occurring within our follow-up window.

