The average EQ-5D utility score for a patient's individual health state will be computed across all utility scores collected during that health state. For instance, EQ-5D scores for all visits during which a grade 3 or 4 adverse event is reported before the patient experiences disease progression on initial treatment will be averaged to form that patient's TOX1 utility score. All EQ-5D scores for visits without either grade 3 or 4 adverse events or disease progression on initial treatment will be averaged to form the patient's TWiST1 utility score. Similar definition and computation apply for TOX2 and TWiST2 with respect to the subsequent treatment. All EQ-5D scores for visits after last disease progression will be averaged to form that patient's PROG utility score. For each health state, the average group utility score is the mean of that health state within each treatment arm.

The restricted mean amount of time for each health state will be estimated using the Kaplan-Meier method, with time limit set at 2 years for computation of all restricted means. The duration of each health state is defined as follows:

- Mean duration of TWiST1 = mean PFS1 – mean TOX1,
- Mean duration of TWiST2 = mean PFS2 – mean TOX2,
- Mean duration of PROG = mean OS – mean PFS2,

where PFS1 is defined as the time from study entry to the first disease progression on the initial treatment. For patients alive without first disease progression, PFS1 will be censored at the date of last disease evaluation in step 1. PFS2 is defined as the time from study entry to the second disease progression on the subsequent treatment (in step 2). For patients enrolled into step 2, if they are alive without disease progression in step 2, PFS2 will be censored at the date of last disease evaluation in step 2. For patients not enrolled into step 2, PFS2 will be censored at the date of last disease evaluation in step 1. OS is defined as the time from study entry to death from any cause, censored at the date of last contact. TOX1 is defined as the days spent with grade 3 or 4 toxicities prior to disease progression on the

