Due to the multiple assessment timepoints for EQ-5D (at baseline, at each cycle while during the initial and subsequent treatment period, then every 3 months up to 2 years from study entry if patients are off protocol treatment and not receiving non-protocol therapy, at end of treatment in each step (before and after crossover), and at dose modification), we do not expect too many patients that reach a state but do not get any EQ-5D evaluation for the utility calculations. If this indeed occurs, it suggests that the reached state is rather short. For the primary Q-TWiST analysis, we assume these data will be missing at random then compute the average group utility weight for each health state based on patients with nonmissing data on the reached

states. If more than 20% of the cases have missing data, with respect to any reached health state, a sensitivity analysis will be performed with missing utility scores on a reached state being replaced by the average EQ-5D utility score from these patients' preceding health state. In case of discrepancies between the primary analysis and the sensitivity analysis, possible explanations will be discussed.

Secondary PRO Analysis. Overall function will be assessed (at baseline, weeks 6 (end of cycle 1), weeks 12 (end of cycle 2), and months 6 (disease stability)) while during the initial and subsequent treatment period (at 6-week, 12-week, months 6, 12, 18, and 24 from study entry (even off study treatment)) using PROMIS PROFILE-29. This instrument, consists of 7 short forms (Depression, Anxiety, Physical Function, Pain Interference, Fatigue, Sleep Disturbance, and Ability to Participate in Social Roles and Activities, with 4 items in each short form) together with one Pain Intensity item. Each item has five response options ranging in value from 1 to 5, except for the Pain Intensity item which has eleven response options ranging in value from 0 to 10. A raw score can be computed for each short form by summing the values of the response to each question within each domain.

The total raw score for each short form can then be converted into a standardized T-score with a mean of 50 and a standard deviation of 10. As to the Pain Intensity item, the raw response (0-10) can be used directly in data analyses.

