Fig 5. Incidence of grade 3-4 AEs. From Sznol et al: "Pooled Analysis Safety Profile of Nivolumab and Ipilimumab Combination Therapy" (5). The percent of patients who experienced at least one grade 3-4 irAE at the respective times (total n=448) are shown [from the original Figure in Ref. (5)]. **Arrows:** time points of **blood collection** in the current study.

Statistical Design and Analysis Plan

Sample Availability Assessed as of July 2020

Overall 90% of the patients consented to participate in the correlative study. We summarized inventory for patients enrolled as of 12/31/19 (as our assessment requires at least 24 weeks of follow-up time) and projected the numbers for the remaining patients.

Aim 1a: Based on the data as of 12/31/19, 90% of the enrolled patients consented to participate in the correlative study. Of the consented patients, 90% had baseline samples and 86% (of the cases submitted baseline samples) had samples on at least one FU time point. At the completion of the study, approximately 104 patients (150X.9X.86) will provide samples for the analysis proposed in Aim 1a. The crossover rate (to arm C or D) was lower than anticipated, but could not be assessed accurately at this point as the study is still being conducted. We project at least 46 patients crossed over to arm D will provide samples for Aim 1a. Therefore, the overall sample size for Aim 1a will be approximately 150 patients.

Aims 1b and 2: As of 12/31/19, approximately 50% of the patients in arm A or D had grade 3 or higher irAEs and submitted samples. Therefore, we project approximately 75 patients will have consented and submitted irAE samples when accrual is completed. The remainder of subjects with less toxicity (~75) will serve as controls.

Study Design and Analysis

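### Routine EQ-5D stops when non-protocol therapy starts, but the Q-TWiST PROG state runs on to death, so the PROG utility comes from a subset selected by post-progression treatment

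*Combined protocol and SAP*

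**What the plan says.** Section 5.9.1 sets the routine schedule as "EQ-5D (5L): every 3 months from study entry up to 2 years", under the heading "Long-Term Follow-up (for patients starting at least one dose of protocol treatment and not receiving any non-protocol therapy". The Assessments text of the same section repeats the condition: "We will conduct all long term follow-up assessments (regardless of still on study treatment given no non-protocol treatment has been" (the sentence ends with the word administered). Section 9.8.2 states it twice more, once where the utility weights are defined and once where missing EQ-5D is discussed: "then every 3 months up to 2 years from study entry if patients are off protocol treatment and not receiving non-protocol therapy".

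Section 9.8.2 defines PROG as the time from the last progression on study to death, with all restricted means cut off at 2 years. Its mean duration is mean OS minus mean PFS2. Its weight is defined by "All EQ-5D scores for visits after last disease progression will be averaged to form that patient's PROG utility score".

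On missing scores, Section 9.8.2 expects few patients to reach a state without any EQ-5D and adds "If this indeed occurs, it suggests that the reached state is rather short". It assumes such data are missing at random. If more than 20% of cases are missing for a reached state, a sensitivity analysis replaces the missing utility with the patient's mean from the preceding state.

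One collection point does not depend on later therapy: an end-of-treatment EQ-5D in each step, whatever the reason for stopping (Section 5.9.1).

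**The concern.** Duration and weight are measured on different populations. All PROG time up to 24 months enters the score, including time on later therapy. The utility that multiplies it comes from three sources only: the interval between progression and the start of later therapy, patients who never receive later therapy, and any end-of-treatment form that falls after progression. Whether a score exists therefore depends on a post-progression treatment decision that is likely to be related to the patient's health.

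This is one of five weights in the primary patient-reported endpoint. The planned bootstrap standard errors describe sampling variation and would not show the problem.

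**Working it through.** **1. The plan's own figures.** The clinically important difference is 10% of a 24-month control median: 0.10 × 24 = 2.4 months. With 135 per group and SD 7 (Section 9.8.1), SE = 7 × √(2/135) = 0.852. Then 2.4/0.852 = 2.817, and power = Φ(2.817 − 1.96) = Φ(0.857) = 0.804, or 0.801 with the noncentral t. The stated 80% reproduces, and the other rows of that table agree within 2 points. No stated figure is wrong.

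**2. How many PROG patients would have a routine score.** The documents give neither the share f of PROG patients who start non-protocol therapy nor the months g from progression to that start. Assume a 3-monthly form falls at random relative to progression, every patient lives to the next form, and the end-of-treatment form is left out. The share with at least one routine PROG score is then (1 − f) + f × min(1, g/3):

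| f | g = 0.5 | g = 1 | g = 2 | g = 3 |
|---|---|---|---|---|
| 0.25 | 79% | 83% | 92% | 100% |
| 0.50 | 58% | 67% | 83% | 100% |
| 0.75 | 38% | 50% | 75% | 100% |
| 0.90 | 25% | 40% | 70% | 100% |

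The range is too wide to say how many patients are affected. Even at 100%, the scores of patients who go on to later therapy are all taken before it starts.

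**3. Effect on one arm.** Error in the arm's score = utility error × mean PROG time. With assumed errors of 0.1 to 0.2 and assumed PROG time of 3 to 6 months, this runs from 0.1 × 3 = 0.3 to 0.2 × 6 = 1.2 months.

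**4. Effect on the comparison.** Bias = e_A × P_A − e_B × P_B, where e is the utility error and P the mean PROG time.
- Equal error in both arms and an assumed 1-month difference in PROG time: 0.1 to 0.2 month, which is 4% to 8% of 2.4.
- Equal PROG time of 3 to 6 months and errors that differ by 0.1: 0.3 to 0.6 month.

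At SD 7 and 135 per group:

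| Net bias (months) | Power if toward the null | Two-sided type I error under the null |
|---|---|---|
| 0.2 | 73% | 5.6% |
| 0.4 | 65% | 7.6% |
| 0.6 | 56% | 10.8% |

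The direction is unknown, so a bias could equally enlarge the apparent difference.

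**5. Do the planned safeguards repair it?**
- *Short-state inference.* A patient whose collection ended by rule soon after progression can remain in PROG until death or 24 months. Absence of a score says nothing about the length of that state.
- *20% trigger.* It appears to count only patients with no score in a reached state. One early form would make a patient non-missing for the whole of PROG.
- *Preceding-state substitution.* This uses a utility from before the last progression. It probably overstates PROG utility, although the documents give no data on this.
- *Zero rule.* Section 9.8.2 assigns 0 to later states after withdrawal or loss to follow-up. It does not say whether collection stopped for non-protocol therapy is handled this way.

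**The case against.** The strongest reply is that the end-of-treatment EQ-5D is due for any reason for stopping, so most patients who stop for progression have a form near that date. It may even fall after it. Section 5.1.5 allows treatment until a confirmatory scan about 4 weeks later while keeping the first scan as the progression date, and footnote 9 of Section 7.1.1 puts the End of Treatment visit 30 days after the last dose. This stands in part. However, the form is triggered by stopping treatment, not by progression. An Arm A patient who completes cycle 14 or stops early for toxicity, progresses later and does not cross over has that form before PROG begins. The plan also does not say whether EQ-5D is taken at the 30-day visit, or whether a form on the progression date counts as after progression.

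A reader might infer that PROG utility is measured only in a minority. The documents do not support that. With f at 50% or less, the table gives 58% or more before any end-of-treatment form is counted. The one relevant background figure points away from frequent later therapy: in the retrospective series cited in Section 1.2, 34 of 176 patients who stopped BRAF-inhibitor therapy received subsequent ipilimumab, and median survival was 2.9 months. The protocol itself calls those data likely biased.

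A reader might also take the Appendix XVI remark, "The crossover rate (to arm C or D) was lower than anticipated", as evidence of widespread non-protocol therapy. The same sentence says the rate could not yet be assessed accurately, and low crossover can also reflect durable control or death.

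Nor does the point carry over simply to the PROMIS comparison. Section 9.8.2 expects differential attrition there and specifies a model for informative censoring.

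**Conclusion.** The mismatch between collection and use is explicit in both sections. Followed as written, the plan yields a PROG utility selected by post-progression treatment. Missing at random is doubtful for patients whose collection stopped by rule, and neither the short-state inference nor preceding-state imputation corrects this.

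The size is not known. The 0.3 to 1.2 months per arm rests on assumed utility errors and assumed PROG durations. It is tempting to divide that by 2.4 and call the result the bias in the endpoint, but it is an error in one arm's score set against a between-arm difference. Only the net difference between arms matters, and the documents give neither its sign nor its magnitude. Crossover rules do differ by direction: Arm A patients must have progressed, Arm B patients need not have, and the steroid conditions differ (Sections 3.2 and 5.1.5). That makes unequal selection possible but does not establish it.

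The point concerns the primary patient-reported objective, which is a secondary objective of the trial. It does not touch the 2-year OS analysis. It should be corrected.

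**What to change.** **Collection.** In Section 5.9.1 (the Long-Term Follow-up heading and the Assessments text) and in both places in Section 9.8.2, remove the no-non-protocol-therapy condition for EQ-5D. Collect it every 3 months to 24 months from study entry in all living treated patients, at the 3-monthly follow-up contacts that Section 7.1.1, footnote 8, already schedules for the first 2 years.

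**Analysis text in Section 9.8.2.**
- Delete the sentence that reads a missing EQ-5D as a sign of a short state.
- For PROG time already unmeasured, stop relying on preceding-state imputation and pre-specify a sensitivity range for the PROG utility, varied separately by arm.
- State whether an end-of-treatment EQ-5D on the progression date counts as PROG.
- Say whether the zero-utility rule applies when collection stopped for non-protocol therapy.
- Report the number and timing of PROG assessments by arm.

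**Cost.** A wording amendment and a short questionnaire for patients otherwise followed only for survival. Those contacts need not be clinic visits, so collection may have to be remote. Section 12 names the electronic PRO system for the tobacco assessment only, so remote EQ-5D entry might need setting up. The documents do not show whether any patient is still within 24 months of entry. If none is, the collection change recovers nothing and the analysis changes carry the whole remedy.

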5.9.2.1 Assessments

Assessments will be captured directly from the participants using the EASEE-PRO portal. When patients consent to participate, they will be asked to provide a contact email address and that address along with their registration information will be sent directly from the parent trial's registration system to EASEE-PRO, and the patient will be automatically registered into EASEE-PRO for participation. To activate their account for self-directed web entry of surveys, the system will send an activation message to the contact email address that will explain how to activate their account for self-directed web entry of surveys. After their account is activated, the patient will be able to complete questionnaires using a secure browser interface from any web enabled computer, tablet, or mobile device.

The Core and Extension C-TUQ items will be assessed, together with patient-reported physical and psychological symptoms (See Table 2). Specifically, these items will be administered using the EASEE-PRO system described in the companion EA NCORP application. The advantage of our virtual electronic data capture system is that our proposed assessments will not be limited to, or dependent

upon, patient trial visits. Confidential and potentially stigmatizing information can be provided without requiring direct contact with the care team.

The selected Core and Extension C-TUQ items (from categories of Basic Tobacco Use Information, Tobacco Use in Relation to Cancer Diagnosis and Treatment, Smoking Cessation/Cessation Products/Assistance Methods, Use of Other Products, and Second-Hand Smoke Exposure) will be assessed. The 4-item Short Form PROMIS® for anxiety and depression, the Lung Cancer Stigma Scale, and six symptom items (general pain, fatigue, nausea, cough, sleep difficulties, shortness of breath) from FACIT (Functional Assessment of Chronic Illness Therapy) together with modifications of these same six questions to address the degree of bother associated with each symptom will be administered as well. Additionally, we will ask participants' perceptions of how smoking improves or worsens each of the six symptom experience. All these items will be compiled into Survey of Tobacco Use (STU). Detailed information on various measures is outlined in [Appendix XIII](#).

Contents and Corresponding Questions in Survey of Tobacco Use (STU)

Dimension	Source of Measures	Baseline STU	Follow-up STU
Basic Tobacco Use Information	C-TUQ	Q1 – Q5	Q1-Q2
Tobacco Use in Relation to Cancer Diagnosis and Treatment	C-TUQ	Q6 – Q7	Q3
Smoking Cessation, Cessation Products, and Assistance Methods	C-TUQ	Q8 – Q13	Q4-Q9
Use of Other Products	C-TUQ	Q14	Q10
Second-Hand Smoke Exposure	C-TUQ	Q15-Q16	Q11-Q12
Psychological Symptoms	PROMIS Lung Cancer Stigma Scale	Q17-Q18	Q13-Q14
Physical Symptoms	FACIT	Q19	Q15
Sociodemographics		Q20-21	

NOTE: In order to minimize ambiguity and assure that patients are oriented to answer appropriately, the specific phrasing of items may vary depending specific cancer type and treatment.

Rev. 5/17

5.9.2.2 Assessment Schedule

Survey of Tobacco Use will be administered at the following time points:

- at baseline (trial enrollment)

- at 3 month follow-up from study registration
- at 6 month follow-up from study registration

5.10 Duration of Therapy

Patients will receive protocol therapy unless:

- Extraordinary Medical Circumstances: If at any time the constraints of this protocol are detrimental to the patient's health, protocol treatment should be discontinued. In this event submit forms according to the instructions in the EA6134 Forms Packet.
- General or specific changes in the patient's condition render the patient unacceptable for further treatment in the judgment of the investigator
- Patient withdraws consent.
- Patient experiences unacceptable toxicity.
- Non-protocol therapies are administered.
- Patient progressed through both step 1 and step 2 study therapies

